Statistical analysis of RNA-Seq expression data derived from samples of the treatment arms will be carried out in the R environment for statistical computing (RDC, 2016). In order to identify differentially expressed genes between the conditions, we will make use voom-limma framework (Ritchie et al., 2015). Briefly, linear models are fit for each gene to estimate the coefficients (= effect size) and their standard error. Empirical Bayes-moderated t-statistics and their associated p-values are then used to assess the significance of the observed expression changes.

In order to evaluate concerted differences of biologically related genes, single sample gene set enrichment will be employed via the GSVA R package (Hanzelmann, Castelo, & Guinney, 2013) which produces a gene-set by sample matrix with approximately normally distributed enrichment scores which can then be compared between treatment arms using for example linear models. Detailed statistical plan is as described in the manuscript [[name], submitted].

Columbia University Irving Medical Center
Herbert Irving Comprehensive Cancer Center
AAAS4165_Version Date: 07/07/2021

4.1.2 Phase 2

The phase 2 portion of the study will be amended after preliminary safety and efficacy results from phase 1 and other ongoing clinical trials have been analyzed and a summary incorporated within the protocol as an amendment including a rationale of the cohorts to be tested. The amendment will be submitted to the Scientific Review Committee (PRMC) and Institutional Review Board (IRB) at CUIMC for approval prior to activation of phase 2 portion of the study.

Three separate phase 2 studies will be conducted based on the differences in baseline response rate by disease subtype:

Cohort 1 – Advanced Pancreas Adenocarcinoma

Cohort 2 – Advanced Colorectal Adenocarcinoma

Cohort 3 – Histology Agnostic Adenocarcinoma

The primary outcome measure is best objective response by 16 weeks; that is, patients who achieve CR or PR within the first 16 weeks will be considered responders. Tumor response will be assessed by CT scans performed every 8 weeks using the Immune-Modified Response Evaluation Criteria in Solid Tumors (IM RECIST). We will use a Simon optimal 2-stage design for each disease subtype to allow for early stopping.

Advanced Pancreas Adenocarcinoma

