4.1.2.2 Analysis of Primary Endpoints

The frequency of best objective response (CR+PR) by 16 weeks will be calculated along with an exact 95% confidence interval.

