| Weight | X | X | X | X | X | X | X | X | X | X | X | X | X | |
| ECOG perf. status | X | X | X | X | X | X | X | X | X | X | X | X | X | |
| ECG ⁶ | X | | | X | | X | | X | | X | | | X | |
| LE Doppler Ultrasound | X | | | | | | | | | | | | | |
| ECHO or MUGA ⁷ | X | | | | | | X | | | | | | X | |
| CBC with differential ⁸ | X | X | X | X | X | X | X | X | X | X | X | X | | |
| Comprehensive metab. panel ⁸ | X | X | X | X | X | X | X | X | X | X | X | X | X | |
| Ophthalmologic exam ⁹ | X | | | | | | | | X | | X | | X | |
| PT/PTT | X | | | X | | | | | | | | | | |
| Fresh tumor biopsy ¹⁰ | X | | | X | | | | | | | | | X | |
| TSH, free T4, cortisol ¹¹ | X | | | | | X | | X | | X | | | X | |
| Viral Serology ¹² | X | | | | | | | | | | | | | |
| C-reactive protein | X | | | | | | | | | | | | | |
| LDH | X | | | | | | | | | | | | | |

Columbia University Irving Medical Center
Herbert Irving Comprehensive Cancer Center
AAAS4165_Version Date: 07/07/2021

| | | | | | | | | | | | | |
|---|---|---|---|---|---|---|---|---|---|---|---|---|
| CPK | X | | | | X | | X | | X | | X | |
| Ca 19-9 and/or CEA | X | | | | X | | X | | X | | X | |
| Pregnancy test ¹³ | X | | | | | | | | | | | |
| Urinalysis | X | | | | | | | | | | | |
| PBMC samples ¹⁴ | X | | | X | | | X | | | | X | |
| Tumor response assessment ¹⁵ | X | | | | | | X | | | | X | |
| Concomitant medications | X | X | X | X | X | X | X | X | X | X | X | |
| Adverse Events | | X | X | X | X | X | X | X | X | X | X | X |
| Atezolizumab administration ¹⁶ | | X | | X | | X | X | X | X | X | X | |
| Dispense cobimetinib | | X | | | | X | | X | | X | | |
| Dispense hydroxychloroquine | | X | | | | X | | X | | X | | |
| Dispense Enoxaparin | | X | | | | X | | X | | X | | |
| Review of dosing diary | | | X | X | X | X | | X | | X | | X |
| Survival follow-up | | | | | | | | | | | | X |
| Blood sampling for PK/PD ¹⁷ | | X | X | X | | X | | | | | | |

1. Protocol-specified screening procedures that are performed as part of standard of care and within 21 days of Day 1 of Cycle 1 may be used for screening purposes. Clinical laboratory studies and baseline CT scan must be performed within the 14-day period before Day 1 of Cycle 1. Screening labs may be used for Cycle 1 Day 1 if performed within 72 hours prior to study visit.
2. The End-of-Study (EOS) visit should be scheduled within the 28-day period after the last dose of study drug and before starting any new anti-neoplastic therapy.

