10. Fresh core tumor biopsy will be performed: (1) within 14 days of starting therapy but at least three days prior to starting therapy; (2) Cycle 1 week 3 (day 15-21); and (3) If the patient allows, at progression (within 4 days of discontinuation of therapy).
11. TSH, free T4, and AM cortisol will be assessed at screening, Day 1 of each cycle starting at C2, at end of study, and as clinically appropriate.
12. At screening, patients without a prior positive HIV test result will undergo an HIV test, unless not permitted per local regulations. Patients will also be tested for HBsAg, HBsAb, total HBcAb, and HCV antibody. If a patient has a negative HBsAg test and a positive total HBcAb test at screening, an HBV DNA test should be performed. If a patient has a positive HCV antibody test at screening, an HCV RNA test must also be performed to determine if the patient has an active HCV infection.
13. For women of child-bearing potential, a screening serum pregnancy test must be negative within 7 days of Day 1 of Cycle 1.
14. Peripheral blood mononuclear cells will be collected during screening, cycle 1 day 15, cycle 3 day 1, every eight weeks (+ 7 days), and at End-of-Service visit.
15. CT scan with contrast of the chest, abdomen, pelvis or CT chest and MRI of abdomen/pelvis, PET/CT, or appropriate imaging of disease site to assess tumor status will be performed. Imaging should be performed at the designated time for tumor assessment +/- 7 days. End of study needs not be performed if patient has radiological evidence confirming progression, but needs to be performed if patient coming off study for other reasons, except due to fatality.
Phase 1 –Imaging to be performed every 8 weeks (+ 7 days)
Phase 2 –Pancreas adenocarcinoma –Imaging to be performed every 8 weeks (+ 7 days)
Colorectal adenocarcinoma – Imaging to be performed every 12 weeks (+ 7 days)
Histology agnostic adenocarcinoma – Imaging to be performed every 8 weeks (+ 7 days)
16. The initial dose of atezolizumab will be delivered over 60 (+/- 15) minutes. Subsequent infusions will be delivered over 30 (+/-10) minutes if the previous infusion was tolerated without infusion-associated adverse events, or 60 (+/- 15) minutes if the patient experienced an infusion-associated adverse event with the previous infusion.
17. For pharmacokinetic (PK) analysis, whole blood for hydroxychloroquine and plasma for cobimetinib will be obtained on –
Cycle 1 Day 1 - Pre-morning dose, 1, 2, and 4 hours post-morning dose.

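### Phase 2 response by week 16: the colorectal scan interval is 8 weeks in one section and 12 in another, and two sets of progression rules score the same patient differently

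*Combined protocol and SAP*

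**What the plan says.** Section 4.1.2 defines the primary outcome for all three Phase 2 cohorts: "patients who achieve CR or PR within the first 16 weeks will be considered responders". It sets one imaging plan, with no exception by cohort: "Tumor response will be assessed by CT scans performed every 8 weeks using the Immune-Modified Response Evaluation Criteria in Solid Tumors (IM RECIST". Section 4.1.2.2 analyses the same quantity: "The frequency of best objective response (CR+PR) by 16 weeks will be calculated along with an exact 95% confidence interval".

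Table 10 footnote 15 keeps 8 weeks for the pancreas and histology-agnostic cohorts but says "Colorectal adenocarcinoma – Imaging to be performed every 12 weeks (+ 7 days".

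On criteria, Table 11 (Section 12.3), 12.4.8 and 12.4.8.4 add measurable new lesions to the tumor burden. They let non-target and non-measurable new lesions bear on CR only. Sections 12.2 and 12.3 bring in RECIST v1.1 only where nothing else is specified. Section 12.8.1 nevertheless counts one or more new lesions as progression. Section 12.8.2 does the same and adds unequivocal non-target progression. Table 12 carries both rules into the overall response. Section 12.9 assigns best response from Tables 12 and 13 and counts it only up to progression. Table 12 also has a confirmation requirement of at least 4 weeks, with a footnote limiting it to non-randomized trials whose primary endpoint is response.

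**The concern.** The primary endpoint is a count of responders, and the plan gives two answers to when patients are scanned and two to how a scan is scored. Two analysts following different sections could report different counts from the same images. The decision rules in Section 4.1.2 turn on few patients: 2/20 then 3/34 in colorectal, 2/23 then 6/56 in histology-agnostic, and 5/23 then 16/67 in pancreas.

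The criteria conflict also works against the plan's own reasoning. Section 12.2 adopts the immune-modified criteria because responses can follow apparent progression or new lesions. Best response assigned through Table 12 would lose some of those responses.

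**Working it through.** **The plan's own figures.** Inputs are the stage sizes, cut-offs and response rates in Section 4.1.2. The probability of a promising result at response rate p is the sum, over stage-1 counts x that pass, of P(X1 = x) × P(stage-2 responders ≥ final cut-off − x). For colorectal at p = 0.15:
- P(X1 = 2 of 20) = 0.2293 and P(X1 ≥ 2) = 0.8244, so P(X1 ≥ 3) = 0.8244 − 0.2293 = 0.5951.
- With X1 = 2, at least one responder is needed among the other 14: 1 − 0.85^14 = 0.897.
- Power = 0.5951 + 0.2293 × 0.897 = 0.801.

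Exact results, against a stated type 1 error of 0.05 and power of 0.80:

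| Cohort | Type 1 error | Power |
|---|---|---|
| Colorectal | 0.0201 | 0.8009 |
| Histology-agnostic | 0.0500 | 0.8003 |
| Pancreas | 0.0472 | 0.8053 |

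The error rates hold as stated. The problem lies in how the count that enters these rules is obtained.

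**Scans by week 16 (nominal weeks).**
- Section 4.1.2, every 8 weeks: weeks 8 and 16, so two.
- Footnote 15, every 12 weeks: week 12, with the next at week 24, so one.

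Footnote 15 can add an end-of-study scan, which "needs to be performed if patient coming off study for other reasons, except due to fatality". That scan depends on leaving the study and is not a routine look.

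**Scoring side by side.**

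| Finding | Table 11, 12.4.8, 12.4.8.4 | 12.8.1, 12.8.2, Table 12 |
|---|---|---|
| Measurable new lesion | Added to burden | PD |
| Non-measurable new lesion | Rules out CR only | PD |
| Unequivocal non-target progression | Bears on CR only | PD |

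Illustration with assumed measurements: the baseline target sum is 100 mm. At week 8 the targets sum to 55 mm and one new 10 mm lesion is present. Burden is 55 + 10 = 65 mm, a change of (65 − 100)/100 = −35%. That passes the 30% threshold, so the patient is PR under Table 11. Table 12 scores any new lesion as PD, and because Section 12.9 stops at progression, a later fall does not restore the response.

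Timing limits the effect. If PR is recorded first and the new lesion appears later, the PR stands under either set, confirmation aside. Only findings at or before the first scan showing the fall change the score.

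**Confirmation.** Four weeks after a first response at week 8, 12 or 16 is week 12, 16 or 20. On routine scans, a week-8 response can be confirmed at week 16. A response first seen at week 16 (8-week interval) or week 12 (12-week interval) has its next routine scan at week 24. Sections 4.1.2 and 4.1.2.2 do not say whether confirmation must fall inside 16 weeks.

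**Effect on a decision.** A colorectal cohort ending on exactly 3 of 34 is promising; with one patient rescored it has 3 − 1 = 2 and is not.

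**The case against.** The strongest reply is that Phase 2 is not open. Sections 1 and 4.1.2 require an amendment and approval before activation, so no Phase 2 patient has been scored under the conflicting text. That stands and limits the urgency. It does not settle the matter: those sections promise a summary of results and a rationale for the cohorts, not a repair of the imaging or response rules.

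A second reply is that the intent is plain. Section 4.1.2 names immune-modified RECIST, and RECIST v1.1 is only a fallback. The intent is indeed evident, but 12.8 and Table 12 are express text, Section 12.9 routes best response through them, and nothing gives Table 11 precedence.

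Third, a cohort-specific interval may be deliberate, and the endpoint can still be measured at week 12. Both points are fair, but then Section 4.1.2 needs the exception. The confirmation point is fairly called a timing gap and not a contradiction.

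Three stronger readings are tempting and are not supported:
- The Table 10 row "Tumor response assessment" might seem a further source for week-8 scans with no colorectal exception. The row carries footnote 15, which is the exception, and its columns are too broken in the available text to place the mark.
- Footnote 15 gives a two-sided window in general and a one-sided one beside each interval. A lost symbol in the PDF reading could produce this, so nothing is built on it.
- A loss of power might be inferred. That needs the share of responders missed or rescored, which the documents do not give. Probabilities of landing on a cut-off describe the design and would be the same in a protocol free of these conflicts.

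**Conclusion.** The point holds as an internal inconsistency that should be fixed before Phase 2 is activated. Two contradictions stand in the current text: the colorectal scan interval, and the rules that turn a new or non-target lesion into progression. The confirmation timing is a secondary gap.

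The demonstrable size is two routine looks against one inside 16 weeks in colorectal, and opposite scores for a definable group of patients in all three cohorts. How many patients fall in that group is unknown, so no change in power or type 1 error is claimed. With cut-offs as low as 2/20 and 3/34, one patient can decide a cohort.

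Phase 1 is touched more lightly. Section 4.1.1.4 reports a best overall response rate without naming criteria, and that Section 12 applies is an inference. The rate is descriptive and drives no decision.

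**What to change.** In the Phase 2 amendment already required:

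1. Reconcile the colorectal imaging interval between Section 4.1.2 and Table 10 footnote 15 so that it supports a 16-week endpoint. An 8-week interval adds scans relative to footnote 15 and none relative to Section 4.1.2.
2. State that, for scoring the primary endpoint and best overall response, Table 11 with 12.4.8 and 12.4.8.4 takes precedence over 12.8.1, 12.8.2 and Table 12.
3. State whether a response must be confirmed and, if so, whether confirmation may come after week 16.

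The precedence statement should be confined to response scoring. Sections 5.5.1 and 7.3 tie progression to stopping treatment, so deleting the progression rules outright would reach further than the endpoint. The sponsor should reconcile any effect of the two definitions on stopping treatment; this review does not choose that rule.

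Apart from any extra colorectal scans, the cost is wording.

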12. MEASUREMENT OF EFFECT

For the purposes of this study, patients should be re-evaluated for progression, as indicated in the schedule of assessments.

12.1 Treatment Beyond Initial Radiographic Progression

In studies of immunotherapeutic agents, complete response, partial response, and stable disease have each been shown to occur after radiographic evidence of an apparent increase in tumor burden. This initial increase in tumor burden caused by immune cell infiltration in the setting of a T-cell response has been termed pseudo-progression (Hales et al., 2010). In Study PCD4989g, evidence of tumor growth followed by a response was observed in several tumor types. In addition, in some responding patients with radiographic evidence of progression, biopsies of new lesions or areas of new growth in existing lesions revealed immune cells and no viable cancer cells. Because of the potential for a response after pseudo-progression, this study will allow patients randomly assigned to immunotherapy-based treatment arms to continue combination treatment after apparent radiographic progression, per immune-modified Response Evaluation Criteria in Solid Tumors (RECIST), provided the benefit-risk ratio is judged to be favorable by the investigator in consultation with the Principal Investigator, and they meet all of the following criteria:

- Evidence of clinical benefit, as determined by the investigator following a review of all available data;
- Absence of symptoms and signs (including laboratory values, such as new or worsening hypercalcemia) indicating unequivocal recurrence of disease;
- Absence of decline in ECOG Performance Status that can be attributed to disease recurrence;
- Absence of tumor recurrence at critical anatomical sites (e.g., leptomeningeal disease) that cannot be managed by protocol-allowed medical interventions;
- Patient's written consent to acknowledge deferring other treatment options in favor of continuing study treatment at the time of initial apparent disease recurrence.

12.2 Rationale for the Use of Immune-Modified RECIST

Increasing clinical experience indicates that traditional response criteria (e.g., RECIST v1.1 and World Health Organization [WHO] criteria) may not adequately assess the activity of immunotherapeutic agents because initial radiographic evidence of disease progression (or in this case, disease recurrence) does not necessarily reflect therapeutic failure. Patients can experience a response in the presence of new lesions or after an increase in tumor burden. Thus, this study will employ immune-modified RECIST for tumor assessments to account for the possible appearance of new lesions and allow radiographic recurrence to be confirmed at a subsequent assessment. It is required that radiographic recurrence be confirmed at a subsequent

tumor assessment to take into account the potential for pseudo-recurrence (caused by immune cell infiltration). Given the proposed immunomodulatory mechanism of action of atezolizumab, and the possibility of observing delayed responses, use of immune-modified RECIST will allow for the capture of a greater proportion of potential responses and allow patients to derive maximum clinical benefit. Immune-modified Response Evaluation Criteria in Solid Tumors (RECIST), as described here, were adapted from RECIST, Version 1.1 (v1.1) (Eisenhauer et al., 2009) in the same manner that immune-related response criteria were adapted from WHO criteria (Wolchok et al., 2009) and RECIST v1.0 (Nishino, Hatabu, Johnson, & McLoud, 2014). When not otherwise specified, RECIST v1.1 conventions will apply. Differences between immune-modified RECIST and RECIST v1.1 are summarized in Table 11.

12.4 Tumor measurability

At baseline, tumor lesions/lymph nodes will be categorized as measurable or non-measurable, as described below. All measurable and non-measurable lesions should be assessed at screening and at subsequent protocol-specified tumor assessment time points. Additional assessments may be performed as clinically indicated when recurrence is suspected.

12.4.1 Definition of measurable lesions

12.4.1.1 Tumor Lesions

Tumor lesions must be accurately measured in at least one dimension (longest diameter in the plane of measurement is to be recorded) with a minimum size as follows:

- 10 mm by CT or MRI scan (CT/MRI scan slice thickness/interval \leq 5 mm);
- 10-mm caliper measurement by clinical examination (lesions that cannot be accurately measured with calipers should be recorded as non-measurable);
- 20 mm by chest X-ray.

12.4.1.2 Malignant Lymph Nodes

To be considered pathologically enlarged and measurable, a lymph node must be \geq 15 mm in the short axis when assessed by CT scan (\leq 5 mm CT scan slice thickness recommended). At baseline and follow-up, only the short axis will be measured and followed. Additional information on lymph node measurement is provided below (see "Identification of Target and Non-Target Lesions," "New Lesions," and "Calculation of Sum of Diameters").

12.4.2 Definition of non-measurable lesions

Non-measurable tumor lesions encompass small lesions (longest diameter $<$ 10 mm or pathological lymph nodes with short axis \geq 10 mm but $<$ 15 mm), as well as truly non-measurable lesions. Lesions considered truly non-measurable include leptomeningeal disease, ascites, pleural or pericardial effusion, inflammatory breast disease, lymphangitic involvement of skin or lung, peritoneal spread, and abdominal mass/abdominal organomegaly identified by physical examination that is not measurable by reproducible imaging techniques.

12.4.3 Special considerations regarding tumor measurability

Bone lesions, cystic lesions, and lesions previously treated with local therapy require particular comment, as outlined below.

12.4.3.1 Bone Lesions:

- Technetium-99m bone scans, sodium fluoride PET scans, and plain films are not considered adequate imaging techniques for measuring bone lesions. However, these techniques can be used to confirm the presence or disappearance of bone lesions.
- Lytic bone lesions or mixed lytic-blastic lesions with identifiable soft tissue components that can be evaluated by cross-sectional imaging techniques, such as CT scan or MRI can be considered measurable lesions if the soft tissue component meets the definition of measurability described above.
- Blastic bone lesions are non-measurable.

12.4.3.2 Cystic Lesions:

- Lesions that meet the criteria for radiographically defined simple cysts should not be considered malignant lesions (neither measurable nor non-measurable) because they are, by definition, simple cysts.
- Cystic lesions thought to represent cystic metastases can be considered measurable lesions if they meet the definition of measurability described above. However, if non-cystic lesions are present in the same patient, these are preferred for selection as target lesions.

12.4.3.3 Lesions with Prior Local Treatment:

Tumor lesions situated in a previously irradiated area or in an area patiented to other loco-regional therapy are usually not considered measurable unless there has been demonstrated progression in the lesion.

12.4.4 Methods for assessing lesions

All measurements should be recorded in metric notation, using calipers if clinically assessed. All baseline evaluations should be performed as close as possible to the treatment start, and never more than 4 weeks before the beginning of the treatment.

The same method of assessment and the same technique should be used to characterize each identified and reported lesion at baseline and during the study. Imaging-based evaluation should always be the preferred option.

12.4.4.1 Clinical lesions

Clinical lesions will only be considered measurable when they are superficial and ≥ 10 mm in diameter, as assessed using calipers (e.g., skin nodules). For the case of skin lesions, documentation by color photography, including a ruler to estimate the size of the lesion, is suggested.

